5.3.5.1 Subgroup Analyses for Primary Endpoint

The generalizability of PFS after randomization results when comparing GDC-9545 compared to physician's choice of endocrine monotherapy will be investigated as a part of exploratory analysis by estimating the treatment effect in subgroups based on factors such as but not limited to:

- Age (<65, ≥65 years)

- Race (American Indian/Alaska native, Asian, Black/African American, Native Hawaiian or Other Pacific Islander, White, Unknown),
- ECOG Performance at baseline (0, 1)
- Menopausal status at baseline (Pre/Peri- Menopausal, Post-Menopausal)
- Hormonal Status (ER+PR+, ER+PR-)
- PFS by ESR1 mutation at baseline (mutation detected, no mutation detected)
- Site of disease assessed locally (visceral, non-visceral)
- Prior treatment with CDK4/6 inhibitor (yes, no),
- Prior treatment with Fulvestrant (yes/no)
- Prior treatment with Aromatase Inhibitor (yes, no)
- Prior treatment with Tamoxifen (yes, no)
- Disease status (Measurable, Non-measurable)
- Number of Organ sites (1, 2, >3)
- Central Nervous System (CNS) involvement (yes, no)
- Bone only involvement (yes, no)
- Previous lines of therapy in the aBC/MBC setting (1, 2)
- Prior Chemo in eBC (yes, no)
- Prior Chemo in aBC/MBC (yes, no)
- Disease Free Interval (≤ 12 months, > 12 months)
- Endocrine Resistance (Primary, Secondary)

Further prognostic factors may be considered for subgroup analyses as deemed appropriate. Un-stratified analysis results will be presented for subgroup analyses due to the potentially limited number of patients in each subgroup. Summaries of PFS after randomization by above subgroups will be provided in forest plots including estimates for HR and 95% CIs from unstratified Cox proportional hazard models.

5.4 SECONDARY ENDPOINTS ANALYSES

The secondary efficacy endpoints for this study Overall Survival (OS), Objective response rate (ORR), Duration of response (DOR), Clinical Benefit Rate (CBR) and PFS in subgroups characterized by baseline ESR1 mutation status and the PROs Time to deterioration (TTD) in pain severity, pain presence/interference, physical functioning, role functioning, global health status and quality of life, are defined in Protocol Section 2.1.2. The subset of corresponding secondary efficacy endpoints which are not derived from patient-reported outcome (PRO) measures, are expressed using the estimand framework. Analysis method for all the secondary endpoints are described in following sub-section.

5.4.1 Overall Survival

The secondary comparison of interest is the hazard ratio of Overall Survival (OS). The secondary trial objective is to demonstrate superiority of the GDC-9545 arm over the physician's choice of endocrine monotherapy treatment arm.

Following the estimand framework (ICH 2020), the attributes of the estimand for the secondary endpoint are defined as follows:

- **Population:** As defined for the primary estimand in section 5.3.1
- **Variable:** Overall Survival (OS), defined as time from randomization to death from any cause.
- **Treatment:** As defined for the primary estimand in section 5.3.1
- **Intercurrent events and Handling strategy**
 - Use of any non-protocol anti-cancer treatment (NPT) prior to disease progression as detailed in Protocol section 4.4.3. → Following treatment policy the ICE will be ignored and observations collected after the ICE will be used.
 - Discontinuation of study treatment prior to disease progression. → Following treatment policy the ICE will be ignored and observations collected after the ICE will be used.
- **Population-level summary:** Hazard ratio for OS.

As per protocol, crossover between treatment arms will not be permitted in the study hence crossover not anticipated as an ICE. If participants have any intercurrent events, then the strategies defined below to handle the intercurrent events will be implemented. Otherwise, data for patients who are alive at the time of the analysis data cutoff will be censored at the last date they were known to be alive. Data from patients without postbaseline information will be censored at the date of randomization plus 1 day.

OS will be hierarchically tested if the primary endpoint, PFS, is statistically significant at the primary PFS analysis. The OS analyses will be conducted at the time of the primary analysis of PFS, at least 12 months after the primary analysis, and at the end of the study, which is expected to occur at least 25 months after the last patient is enrolled in the global study, refer to section 5.8 for details on interim analysis for OS.

5.4.2 Overall Response Rate

The analysis population for ORR will be full analysis set. Patients not meeting the criteria for ORR, including patients without any postbaseline tumor assessment, will be considered non-responders.

Following the estimand framework (ICH 2020), the attributes of the estimand for the secondary endpoint are defined as follows:

- **Population:** As defined for the primary estimand in section 5.3.1.
- **Variable:** ORR, defined as the proportion of patients with a CR or PR on two consecutive occasions ≥ 4 weeks apart, as determined by the investigator according to RECIST v1.1.
- **Treatment:** As defined for the primary estimand in section 5.3.1

- **Intercurrent events and Handling strategy:**
 - As described for the primary estimand in section 5.3.1.
 - **ICE Handling Strategy:**→ Following treatment policy, all the ICE's will be ignored and tumor assessment data collected after the ICE will be included in the ORR analysis.
- **Population-level summary:** Difference in proportion.

An estimate of ORR and 95% CI will be calculated using the Clopper-Pearson method for each treatment arm. ORR will be compared between treatment arms using the stratified Cochran-Mantel-Haenszel test. The stratification factors to be used will be the same as those used for the analysis of the primary endpoint. The difference in ORR between treatment arms will be calculated, and 95% CI will be calculated using the Newcombe methodology (Newcombe 1998).

5.4.3 **CBR**

Following the estimand framework (ICH 2020), the attributes of the estimand for the secondary endpoint are defined as follows:

- **Population:** As defined for the primary estimand in section 5.3.1
- **Variable:** CBR, defined as the proportion of patients with stable disease for ≥ 24 weeks or a CR or PR, as determined by the investigator according to RECIST v1.1.
- **Treatment:** As defined for the primary estimand in section 5.3.1
- **Intercurrent events and Handling strategy:**
 - As described for the primary estimand in section 5.3.1
 - **ICE Handling Strategy:**→ Following treatment policy, all the ICE's will be ignored and tumor assessment data collected after the ICE will be included in the CBR analysis.
- **Population-level summary:** Difference in proportion.

CBR analysis including handling of ICE will follow the same methods as those used for ORR.

5.4.4 **DOR**

Analysis of DOR will include only patients who had an objective response.

Following the estimand framework (ICH 2020), the attributes of the estimand for the secondary endpoint are defined as follows:

- **Population:** All randomized patients who had an objective response.
- **Variable:** DOR, defined as the time from the first occurrence of a documented objective response to disease progression or death from any cause (whichever occurs first), as determined by the investigator according to RECIST v1.1.

- **Treatment:** As defined for the primary estimand in section [5.3.1](#)
- **Intercurrent events and Handling strategy**
 - As described for the primary estimand in section [5.3.1](#).
 - **ICE Handling Strategy:**→ Following treatment policy, all the ICE's will be ignored and tumor assessment data collected after the ICE will be included in the DOR analysis.
- **Population-level summary:** Hazard ratio.

Handling of ICE will follow the same methods as those used for PFS. Data for patients who have not progressed and who have not died at the time of analysis will be censored at date of the last tumor assessment. The Kaplan-Meier approach will be used to estimate the median DOR and to construct survival curves for each treatment arm for a visual description of the difference among arms. The [Brookmeyer-Crowley](#) methodology will be used to construct the 95% CI for the median ([Brookmeyer and Crowley 1982](#)).

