4.5.6.2 Postbaseline Tumor Assessments

Postbaseline tumor assessments will be performed according to the schedule below, from randomization, regardless of dose delay, until radiographically and/or clinically (i.e., for photographed or palpable lesions) disease progression as assessed by the investigator according to RECIST v1.1 (see [Appendix 4](#)), except in the case of isolated brain metastases as described in Section 4.4.3. Thus, tumor assessments are to continue according to schedule in patients who discontinue treatment for reasons other than disease progression, even if they start new anti-cancer therapy. For patients with symptomatic deterioration, every effort should be made to provide documented progression via radiographic modality. Tumor assessments should be scheduled relative to the date of randomization rather than the date of the previous tumor assessment.

The following postbaseline tumor assessments will be performed every 8 weeks (± 7 days) from randomization for the first 18 months, then every 12 weeks (± 7 days) thereafter:

- CT or MRI scan of the chest, abdomen, and pelvis
- CT or MRI scan of brain if clinically indicated
- CT or MRI scan of any other sites of disease identified at baseline
- Clinical assessment of sites of superficial disease identified at baseline
- For patients with bone lesions at baseline: X-ray, CT scan, or MRI scan of selected evaluable bone lesions, ensuring consistent use of the same modality for all evaluations

Bone scans are required to confirm CR; however, areas that have received palliative radiotherapy during the study cannot be used to assess response to study treatment.

Postbaseline bone scans will be performed every 24 weeks (± 7 days) or as clinically indicated.

At the investigator's discretion, tumor assessments may be repeated at any time if progressive disease is suspected.

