4.6 TREATMENT, PATIENT, STUDY, AND SITE DISCONTINUATION

4.6.1 Study Treatment Discontinuation

Patients must permanently discontinue study treatment if they experience any of the following:

- Any medical condition that the investigator or Sponsor determines may jeopardize the patient's safety if he or she continues to receive study treatment
- Investigator or Sponsor determination that treatment discontinuation is in the best interest of the patient
- Intolerable toxicity related to study treatment determined by the investigator to be unacceptable in light of the potential for treatment benefit and the severity of the event
- Disease progression per investigator assessment according to RECIST 1.1, with the exception of isolated brain metastases (see Section 4.4.3)
- Symptomatic deterioration attributed to disease progression, as assessed by the investigator
- Non-compliance with protocol-specified drug administration and follow-up tests
- Concomitant use of any other (non-protocol) systemic anti-cancer therapy
- Pregnancy

The primary reason for study treatment discontinuation should be documented on the appropriate eCRF. Patients who discontinue study treatment will not be replaced.

Patients will return to the clinic for a treatment discontinuation visit 30 (+3) days after the final dose of study treatment (unless final dose resulted in a dose delay prior to decision to discontinue). For the control arm, the upper limit of the visit window will be dependent upon maximum dosing delay as permitted per local guidelines. The visit at which response assessment shows progressive disease may be used as the treatment discontinuation visit if it falls within 28 (+3) days after the patient's final dose of study treatment. After treatment discontinuation, adverse events will continue to be recorded as outlined in the schedule of activities (see [Appendix 1](#)).

Patients who discontinue study treatment for any reason other than unequivocal disease progression or death will continue to undergo tumor response assessments and PRO assessments as outlined in the schedule of activities (see [Appendix 1](#)).

After treatment discontinuation (regardless of the reason), information on survival follow-up and new anti-cancer therapy will be collected via telephone calls,

patient medical records, and/or clinic visits approximately every 6 months or more frequently until death (unless the patient withdraws consent or the Sponsor terminates the study).

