5.3.1 Definition of Primary Estimand

Following the estimand framework introduced in the ICH-E9 addendum ([ICH 2020](#)), the attributes of the estimand built around the primary endpoint are defined as follows:

- **Population:** Patients with previously treated estrogen receptor (ER)-positive, HER2-negative locally advanced or metastatic breast cancer who have received one or two prior lines of systemic therapy in the locally advanced or metastatic setting, as defined by the inclusion / exclusion criteria in study protocol (refer to Protocol section 4.1)
- **Variable:** Progression Free Survival (PFS), defined as time after randomization to the first occurrence of disease progression or death from any cause (whichever occurs first), as determined by the investigator according to RECIST v1.1
- **Treatment:** GDC-9545 or physician's choice of endocrine monotherapy. During the conduct of the study, participants may also receive concomitant medications as detailed in Protocol section 4.4.

- **Intercurrent events and Handling Strategy:**
 - Use of any non-protocol anti-cancer treatment (NPT) prior to disease progression as detailed in Protocol section 4.4.3. → Following treatment policy the ICE will be ignored and tumor assessment data collected after the ICE will be included in the PFS analysis
 - Discontinuation of study treatment prior to disease progression → Following treatment policy the ICE will be ignored and tumor assessment data collected after the ICE will be included in the PFS analysis.
- **Population-level summary:** Hazard ratio

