5.3.5 Supplementary Analyses for Primary Endpoint

Two supplementary analysis as outlined below based on different strategy of handling ICE are planned for PFS. Note that the attributes of population, variables and population level summary will remain the same as the primary estimand. The analysis for the supplementary estimands will be conducted only on the primary endpoint investigator assessed PFS.

1. **PFS assessed by investigator based on hypothetical strategy for use of any NPT prior to disease progression:** → To assess the impact of use of any NPT prior to disease progression, the primary analysis of investigator assessed PFS will be repeated with the ICE of use of any NPT handled using a hypothetical strategy. According to this strategy, patients who start NPT prior to disease progression will be censored at the time of the last disease status assessment before the initiation of NPT. If patients start any NPT before starting study treatment then the data of those patients will be censored at the time of randomization plus day 1. Approaches to handle other ICE (Discontinuation of study treatment prior to disease progression) and analysis method will be the same as mentioned in section [5.3.2](#).
2. **PFS assessed by investigator based on composite strategy for use of any NPT prior to disease progression:** → In addition to above estimand, here supplementary estimand for PFS will be estimate by following composite strategy. According to composite strategy, use of any NPT prior to disease progression will be considered as PFS event (progressed) at the time of initiation of NPT. If patients start any NPT before starting study treatment then the data of those patients will be censored at the time of randomization plus day 1. Approaches to handle other ICE (Discontinuation of study treatment prior to disease progression) and analysis method will be the same as mentioned in section [5.3.2](#).

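### ORR and CBR count responses and stable disease reached on another systemic anti-cancer drug, and no analysis checks this

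*SAP*

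**What the plan says.** SAP 5.3.1 names two intercurrent events: "Use of any non-protocol anti-cancer treatment (NPT) prior to disease progression as detailed in Protocol section 4.4.3" and "Discontinuation of study treatment prior to disease progression". SAP 5.4.2 carries both over to ORR: "Following treatment policy, all the ICE's will be ignored and tumor assessment data collected after the ICE will be included in the ORR analysis". SAP 5.4.3 repeats this for CBR, so that "tumor assessment data collected after the ICE will be included in the CBR analysis". Neither variable requires the CR, PR or 24 weeks of stable disease to come before NPT.

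The scans exist. Protocol 4.5.6.2 continues scheduled tumour assessments until progression "in patients who discontinue treatment for reasons other than disease progression, even if they start new anti-cancer therapy". Protocol 4.6.1 lists "Concomitant use of any other (non-protocol) systemic anti-cancer therapy" among the reasons for permanent discontinuation of study treatment.

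SAP 5.3.5 sets out a hypothetical and a composite analysis for NPT, then limits them: "The analysis for the supplementary estimands will be conducted only on the primary endpoint investigator assessed PFS".

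**The concern.** ORR and CBR are secondary efficacy endpoints, and the sponsor's own text reads such rates as activity of the drug. Protocol 3.3.1 cites CBR as the measure of clinical activity at the chosen dose, and Protocol 1.2.2.2 attributes the higher ORR and CBR to giredestrant. A response that first appears on a later systemic agent is not evidence of that activity.

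The sponsor already guards against the local equivalent. Protocol 4.5.6.2 does not let areas given palliative radiotherapy on study contribute to response assessment, and Protocol 4.4.3 makes irradiated target or non-target lesions un-evaluable. Systemic therapy, which can shrink every lesion, has no such guard in ORR or CBR.

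NPT can turn a failure into a success in a binary endpoint, yet only PFS has alternative analyses. DOR (SAP 5.4.4) inherits the issue, because its population is the responders and its clock can start at a response reached on NPT. At stake is how cleanly the secondary activity comparison can be read, not the primary claim: SAP 2.1 tests PFS then OS, and ORR and CBR lie outside that hierarchy.

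**Working it through.** **1. The chain in the text.** (a) A patient stops study drug without RECIST progression. Protocol 4.6.1 gives routes such as intolerable toxicity, investigator or sponsor decision, and symptomatic deterioration; Protocol Appendix 4 says the last is not an objective response category. (b) She starts another systemic agent, and under Protocol 4.6.1 the randomised drug is then off. (c) Protocol 4.5.6.2 keeps scanning her. (d) A confirmed CR/PR on those scans counts under SAP 5.4.2; the same CR/PR, or scans completing 24 weeks of stable disease, counts under SAP 5.4.3. (e) Protocol 6.4.2.2 and 6.4.2.4 contain no NPT rule that would exclude it, and SAP section 5 says the SAP's analyses take precedence over the Protocol's.

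**2. Reported figures.** The plan gives no power or sample size for ORR or CBR. Protocol 1.2.2.2 reports ORR 12.6% vs 7.2% and CBR 31.8% vs 21.1% in 303 patients. Trying experimental-arm sizes from 140 to 163, with the control arm as 303 minus that size, only 151 and 152 reproduce all four percentages to one decimal:

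- ORR: 19/151 = 12.6%, 11/152 = 7.2%; difference 5.3 points (5.4 from the rounded rates).
- CBR: 48/151 = 31.8%, 32/152 = 21.1%; difference 10.7 points.

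These counts are back-solved, on the assumption that all 303 patients form the denominators.

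**3. Reclassification for scale.** Suppose k_E experimental and k_C control successes were first reached on NPT and are rescored as failures. The difference then changes by −k_E/151 + k_C/152. For two patients in one arm this is 2/151 = 1.3 points down, or 2/152 = 1.3 points up. Intervals are unstratified Newcombe.

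| Endpoint | Rescored | Counts | Difference (95% CI), points |
|---|---|---|---|
| ORR | none | 19/151 vs 11/152 | 5.3 (−1.5 to 12.3) |
| ORR | 2 experimental | 17/151 vs 11/152 | 4.0 (−2.7 to 10.8) |
| ORR | 2 control | 19/151 vs 9/152 | 6.7 (0.1 to 13.5) |
| ORR | 2 in each arm | 17/151 vs 9/152 | 5.3 (−1.1 to 12.0) |
| CBR | none | 48/151 vs 32/152 | 10.7 (0.8 to 20.4) |
| CBR | 2 experimental | 46/151 vs 32/152 | 9.4 (−0.4 to 19.0) |
| CBR | 3 control | 48/151 vs 29/152 | 12.7 (2.9 to 22.2) |

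The k values are hypothetical; they show sensitivity, not what happened.

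**4. The only related count.** Protocol 1.2.2.2 gives treatment withdrawals for adverse events as 2 (GDC-9545) and 3 (control). At the extreme, all five started NPT before progression and are counted as responders only because of it. ORR would then be 17/151 vs 8/152, a difference of 6.0 points (−0.3 to 12.6). If it were true of the two experimental patients alone the difference would be 4.0; of the three control patients alone, 7.3. Other routes are not counted anywhere in the documents.

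**The case against.** Treatment policy is explicit in the SAP, with full estimands, and is applied alike to PFS, OS, ORR, CBR, DOR and PFS by ESR1 status. A difference in proportions under that strategy is a coherent comparative estimand. This stands: the SAP does not contradict itself.

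The route is also narrow. Protocol 4.4.3 prohibits other anti-cancer therapy until progression is documented and study treatment has stopped. Scheduled scans end at progression. Sites are to make every effort to document progression when a patient deteriorates symptomatically. ORR needs a second confirming assessment. Under Protocol 4.6.1, patients unwilling to return to the clinic have no further tumour assessments, so they cannot gain a late response. This stands as well, and is why the number is probably small.

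Two stronger readings are tempting. One is that control patients in an open-label trial switch earlier, so control rates are inflated more and the treatment difference shrinks. The documents give neither switching counts by arm nor response rates on NPT, so no direction can be claimed. The other is that patients who never took study drug are being counted as responders. SAP 5.3.5 mentions NPT started before study treatment only as a contingency, and Protocol 4.3.2 puts the first dose no later than 3 days after randomisation; neither shows that this occurred.

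Finally, primary-analysis rates are already reported. Replacing the main ORR and CBR estimands now would be post hoc, would break alignment with the other endpoints, and in an open-label trial would turn a decision to switch into a failure. That argues for adding an analysis, not substituting one. It does not explain why PFS has two NPT analyses and ORR and CBR have none.

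**Conclusion.** The point holds as a gap in supporting analyses. Successes first reached on another systemic drug before RECIST progression count for the randomised arm in ORR and CBR, DOR inherits those responders, and nothing planned shows how much this matters. The size is unknown: about 1.3 points on the ORR difference for every two responders in one arm, in either direction, assuming the back-solved counts are right. A few patients could move a nominal interval across zero, but nothing shows that they did. The primary claim and its error control are unaffected. This is a cheap improvement, not a flaw that invalidates the reported rates.

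**What to change.** Add to SAP 5.4.2 and 5.4.3 an analysis that counts CR/PR, or stable disease for at least 24 weeks, only if reached before the start of systemic NPT. Score other NPT starters as non-responders. State that permitted local palliative radiotherapy does not trigger the rule; this is needed because the SAP defines NPT by reference to Protocol 4.4.3, which also covers radiotherapy.

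Report it beside the all-data analysis. Give by arm the number of patients who started NPT before progression and the number who first responded afterwards; those two counts alone would settle how much the point matters. Label the analysis post hoc for the primary-analysis cutoff already reported.

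Cost: SAP wording and a little more analysis work. No new data are needed, since Protocol 4.6.1 collects new anti-cancer therapy and SAP 5.3.5 already requires NPT start timing for PFS. The rates in the added analysis may be slightly lower.

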3.3.2 Rationale for Patient Population

The target patient population for this study is women and men with ER-positive, HER2-negative locally advanced or metastatic breast cancer who have received one or two prior lines of systemic therapy in the locally advanced or metastatic setting.

Endocrine therapies are the mainstay of treatment for HR-positive breast cancer, but many patients relapse during endocrine therapy, which ultimately limits the use of these agents. However, tumors continue to depend on ER activity for growth, and ER remains an important target in the endocrine-resistant setting, emphasizing the need for more effective endocrine treatment. Patients previously treated with fulvestrant are eligible for this study, given that GDC-9545 was more efficacious than fulvestrant in xenograft models of ER-positive breast cancer, when dosed according to a clinically relevant dosing scheme. Furthermore, as of the CCOD of 31 January 2021 in Study GO39932, clinical benefit (confirmed CR, PR, or the first occurrence of PD on or after 24 weeks) was observed for 8 of 26 (30.8%) clinical benefit-evaluable patients treated with single-agent GDC-9545 at various dose levels after prior treatment with fulvestrant.

Hence, the patient population defined by the eligibility criteria reflects patients for whom there is an unmet medical need, as the current standard of care treatment options are limited.

Both postmenopausal and premenopausal/perimenopausal women will be included in the study. Premenopausal/perimenopausal women will receive an LHRH agonist for ovarian function suppression. Male patients will also receive an LHRH agonist.

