6.4.2.4 Clinical Benefit Rate

CBR, defined as the proportion of patients with stable disease for ≥ 24 weeks or a CR or PR, as determined by the investigator according to RECIST v1.1. CBR will be analyzed using the same methods as those used for ORR.

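### The response limb of CBR needs no confirmation, so a single PR at Week 8 followed by PD at Week 16 counts as clinical benefit although ORR calls the same patient a non-responder (minor)

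*SAP*

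**What the plan says.** SAP 5.4.3 gives the CBR variable as "CBR, defined as the proportion of patients with stable disease for ≥ 24 weeks or a CR or PR, as determined by the investigator". Protocol 6.4.2.4 has the same content: "stable disease for ≥ 24 weeks or a CR or PR, as determined by the investigator according to RECIST v1.1". Protocol 2.1.2, the protocol synopsis and SAP Table 1 repeat it.

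ORR, in SAP 5.4.2, is stricter. It requires "CR or PR on two consecutive occasions ≥ 4 weeks apart, as determined by the investigator".

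One sentence in SAP 5.4.3 links the two endpoints: "CBR analysis including handling of ICE will follow the same methods as those used for ORR".

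Protocol 4.5.6.2 sets the scan schedule: "The following postbaseline tumor assessments will be performed every 8 weeks", with a window of 7 days either side, for the first 18 months. The RECIST text in Protocol Appendix 4 classifies response at a single timepoint. As reproduced there, it contains no confirmation rule and no rule for best overall response.

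**The concern.** The trial is open-label and CBR is read by the investigator. Under the wording above, one scan read as PR is enough for a CBR success, whatever the next scan shows. The second reading that guards ORR against a chance or over-called PR does not guard CBR. The rate can therefore include patients who progressed well before 24 weeks and whom the same SAP counts as non-responders.

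What is at stake is the meaning of a descriptive secondary endpoint. CBR lies outside the PFS-then-OS testing sequence in SAP 2.1, so neither the primary conclusion nor its type I error is involved.

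**Working it through.** **1. Apply the wording to one record, scheduled scans only.** PR at Week 8 (window Weeks 7 to 9), PD at Week 16 (window Weeks 15 to 17).

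- ORR: one PR followed by PD is not two consecutive responses. Non-responder.
- PFS: event at about 16 weeks, 17 at most, which is below 24.
- CBR: the patient has had a PR. Counted.

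An unscheduled scan that again showed PR at least 4 weeks after the first, before the PD, would make the patient an ORR responder too. The example assumes there was none.

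**2. What the reported results can and cannot show.** Protocol 1.2.2.2 reports 303 patients, CBR 31.8% vs 21.1% and ORR 12.6% vs 7.2%. Trying splits from 148/155 to 155/148, only 151/152 reproduces all four percentages:

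- CBR: 48/151 = 31.8%, 32/152 = 21.1%, difference 10.7 points.
- ORR: 19/151 = 12.6%, 11/152 = 7.2%.
- CBR but not ORR: 48 − 19 = 29 vs 32 − 11 = 21.

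Those 29 and 21 patients mix stable disease of at least 24 weeks with unconfirmed responses. The documents do not separate them, so the effect of the wording on the reported difference cannot be computed.

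For scale only, take an unstratified pooled z-test. The pooled rate is 80/303 = 0.264, SE = √[0.264 × 0.736 × (1/151 + 1/152)] = 0.0507, z = 0.1074/0.0507 = 2.12, p = 0.034. Now remove hypothetical unconfirmed early progressors (experimental vs control):

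| Removed | Difference (points) | p |
|---|---|---|
| 3 vs 0 | 8.7 | 0.080 |
| 5 vs 0 | 7.4 | 0.134 |
| 3 vs 3 | 10.7 | 0.030 |
| 8 vs 8 | 10.7 | 0.022 |

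Equal removal leaves the difference as it is. Only an imbalance between arms would matter.

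**3. Illustrative size of the excess in the rate.** A simulation of 400,000 patients per setting, scans at Weeks 8, 16 and 24. The only inputs from the documents are the scan interval, the RECIST thresholds (PR: at least 30% below baseline; PD: at least 20% above the smallest sum) and the design medians of 5.5 and 8.5 months. The rest is assumed:

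- linear log change in the sum of diameters, mean 0, SD 0.10 or 0.15 per 8 weeks;
- measurement CV of 7, 10 or 15%;
- exponential non-target or new-lesion progression with median 1.3 times the design median.

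Excess = CBR with any PR accepted, minus CBR with PR required at two consecutive scans, in percentage points across both medians and both SDs:

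| CV | First PD at Week 24 counts as benefit | It does not |
|---|---|---|
| 7% | 0.07 to 0.33 | 0.55 to 1.57 |
| 10% | 0.41 to 0.75 | 1.30 to 2.25 |
| 15% | 2.40 to 2.58 | 4.79 to 5.07 |

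The model gives every patient a sum of diameters. Bone-only disease is eligible under Protocol 4.1.1, and Appendix 4 has no PR category for patients with non-target lesions only. If 75% had measurable disease (an assumption), the largest row scales to about 0.75 × 4.79 = 3.6 up to 0.75 × 5.07 = 3.8 points.

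**The case against.** The strongest reply is that the SAP already ties CBR to the ORR methods, so a programmer might carry the confirmation rule across. That is possible, but the sentence concerns analysis and intercurrent events, and the CBR variable is stated separately without confirmation. If both readings are open, the text permits two derivations of one endpoint, which is itself a reason to settle it.

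A second reply has more force. The trial's documents define clinical benefit consistently as a response or 24 weeks of stable disease. Protocol 4.4.3 uses the same form, and nothing says that CBR must measure durable control. An unconfirmed response limb is therefore a permissible choice and not a contradiction. This stands, and it is why the point is minor.

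A reader might infer more from three places, and the documents do not support it:

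- **That the wording departs from the sponsor's earlier definition.** Protocol 3.3.2 does describe benefit in Study GO39932 as "confirmed CR, PR, or the first occurrence of PD on or after 24 weeks", though it is arguable whether the first word governs PR. Protocol 1.2.2.1 describes benefit in that same study as radiographic PR or at least 6 months of stable disease, with no mention of confirmation. There is no single earlier definition to depart from.
- **That CBR ranks longer control below shorter.** The tempting comparison is a patient with stable disease at Weeks 8 and 16 and PD at Week 24. Whether that patient counts is not stated for this trial, and the wording in Protocol 3.3.2 would count the patient as benefit.
- **That the reported CBR difference is an artefact.** No count of unconfirmed responders by arm is given, and unbiased reading would inflate both arms alike.

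**Conclusion.** The point holds as a minor one. On the wording of both documents, a single unconfirmed CR or PR makes a patient a CBR success even if progression follows before 24 weeks, while ORR in the same SAP rejects that response.

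Its size is unknown from the documents. Under the assumptions shown, the rate is raised by about 0.1 to 2.6 points if first progression at Week 24 counts as benefit and by up to about 5 points if it does not. The upper values need a measurement CV of 15%. The excess is close to equal in the two arms when reading is unbiased, so it would affect the absolute rates more than the difference. A tendency to over-read PR in one arm would pass directly into the difference, but nothing in the documents shows that this happened. The PFS and OS conclusions are unaffected.

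**What to change.** In SAP 5.4.3, and in Protocol 2.1.2 and 6.4.2.4 to match:

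- Define the response limb of CBR as a confirmed CR or PR on the ORR rule: two consecutive occasions at least 4 weeks apart.
- Count an unconfirmed CR or PR as stable disease toward the 24 weeks.
- Keep the existing stable-disease limb. Replacing it with absence of progression would be a separate change of endpoint, because it would bring in patients with non-target disease only who are classed as neither CR nor PD.
- State how a first PD at the Week 24 scan, with its 7-day window either side, is classified. The illustrative excess at least halves or doubles on this choice.

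Protocol version 4 already reports CBR by arm, so redefining it for that cutoff would be post hoc. For that cutoff, leave the reported CBR in place, add the confirmed-response CBR as a labelled sensitivity analysis, and report by arm the number of unconfirmed responders with PD before 24 weeks. That count would settle the size.

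The cost is a few sentences and one extra table, with no new data. CBR falls slightly, and a patient whose first PR is at the last scan before the cutoff is not credited until the response is confirmed or 24 weeks are reached.
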